- 5) meeting hazardous drinking criteria on the AUDIT-C questionnaire, defined as a score of 3 or higher for women/4 or higher for men (The AUDIT-C consists of items 1, 2, and 3 from the full AUDIT questionnaire);

Participants with severe psychopathology (psychosis, suicidal behavior, substance dependence) will be excluded from the study. The AUDIT questionnaire will be administered as part of screening to determine alcohol dependence; if survivors have a score of 20 or higher, they will be referred to UKMCC Social Work.

**RCT:** n=50, Intervention group (TRAC) n=25, and Control group (education and monitoring) n= 25. To be eligible to participate in the RCT, survivors must meet the following criteria:

- 1) diagnosed with cancer between age 15-39;
- 2) currently age 18-39;
- 3) 3 months - 15 years posttreatment (hormonal therapy allowed);
- 4) report unhealthy alcohol use in the previous 3 months, defined as:
  - a. exceeding moderate daily drinking levels (more than 1 drink/day for women, more than 2 drinks/day for men) at least 3 times in the past 3 months OR
  - b. engaging in heavy weekly drinking (more than 7 drinks/week for women, more than 14 drinks/week for men) at least once in the past 3 months OR
  - c. engaging in binge drinking (more than 3 drinks/sitting for women, more than 4 drinks/sitting for men) at least once in the past 3 months; OR
- 5) meeting hazardous drinking criteria on the AUDIT-C questionnaire, defined as a score of 3 or higher for women/4 or higher for men (The AUDIT-C consists of items 1, 2, and 3 from the full AUDIT questionnaire)
- 5) Reside in the United States

Just as with the Open Pilot, participants with severe psychopathology will be excluded from the study. The AUDIT questionnaire will be administered as part of screening to determine alcohol dependence; if survivors have a score of 20 or higher, they will be referred to UKMCC Social Work (if a patient at UK HealthCare). Non-UK patients will be provided with information for SAMHSA's treatment finder, national helpline, and local resources based on the zip code provided at the time of screening. Survivors who score a 20 or higher on the AUDIT questionnaire will not be eligible for the study, as this study is not designed to manage alcohol dependence and its immediate health risks.

Enrollment will begin February 2022 and continue through May 2023 or until the proposed participant pool is reached.

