## Objectives

List your research objectives. Please include a summary of intended research objectives in the box below.

Posttreatment rural AYAs are an underserved group at risk for increased alcohol use and poor access to interventions, ultimately leading to poorer physical and mental health. mHealth interventions are recommended for AYAs and have shown high acceptability and positive health effects. To address the lack of mHealth interventions for alcohol use among rural AYAs, we will adapt and pilot an existing mHealth intervention (TRAC) to reduce alcohol use. We will conduct the study in Kentucky, which leads the nation in cancer incidence and mortality, has a higher incidence of AYA cancers compared to other states, is 40% rural, and encompasses over 100 medically underserved areas. The study team has expertise in mHealth interventions, cancer survivorship, clinical trials, and AYA oncology. Thus, we are well-equipped to complete the following Aims:

1. Adapt and refine TRAC for rural posttreatment AYAs. We will conduct semi-structured interviews with key informants (N=14; 6 AYAs, 8 AYA oncology clinicians and community advocates), and conduct an open pilot study (i.e., fully implement the intervention) with a small number of patients (N=4; 2 TRAC, 2 control comparison) to adapt the content and delivery procedures of TRAC for rural AYA cancer survivors, resulting in TRAC-AYA.

2. Test the feasibility and acceptability of conducting an RCT of TRAC-AYA with AYAs (N=50; 25 TRAC, 25 control comparison). Comparison group will receive alcohol monitoring and educational materials. The primary feasibility outcome will be enrollment (=60% of eligible AYAs approached enroll). Secondary feasibility outcomes include retention (=60% complete follow-up) and intervention adherence (=70% complete =60% of intervention sessions; alcohol monitoring =70%). Acceptability will be assessed with mean ratings (scores =7 out of 10) of intervention relevance, helpfulness, and convenience. We will also obtain preliminary data on alcohol use frequency, quantity, binge drinking, and health (PROMIS-29).

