#### Study Procedures: Randomized Controlled Trial

To achieve Aim 2, we will conduct a pilot RCT of the TRAC-AYA intervention with a total of 50 participants (25 per condition).

Participants in the RCT will be enrolled in the study for a total of 10 weeks, whether they are in the intervention or control group. If participants are unable to complete monitoring or intervention tasks within the initial 4-week period, they will be given up to 6 weeks to complete the tasks before being considered noncompleters. The delayed post-test is delivered 4 weeks after completion of all monitoring/intervention tasks at 10 weeks.

Intervention (Group A) participants will complete 4 intervention sessions on a weekly basis, conducted via phone or videoconference (HIPAA-compliant Zoom), according to participant preference. These sessions will be audio recorded. Participants will also complete daily self-monitoring of alcohol use using mobile surveys and breathalyzers for 6 weeks. Control (Group B) participants will receive educational materials regarding alcohol use and will complete mobile monitoring of alcohol use in the same manner as Group A for 6 weeks. All RCT participants will complete a baseline assessment survey upon enrollment, a follow-up survey once all intervention/monitoring tasks are completed at 6 weeks, and a qualitative exit interview which will be audio recorded. All RCT participants will also complete a delayed post-test assessment at 10 weeks, 4 weeks after they complete the follow-up survey.

The total estimated maximum time commitment for RCT Group A (Intervention) participants is 13 hours, 45 minutes. The total estimated maximum time commitment for RCT Group B (Control) participants is 10 hours, 45 minutes.

All RCT participants will receive up to \$315 in Amazon e-gift cards for their participation.

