**RCT Data Collection:** For Group A (Intervention) participants only, a brief treatment expectations questionnaire assessing their attitudes toward the intervention will be administered. Additionally, after each counseling session, Group A participants will complete a short intervention session rating questionnaire. All counseling sessions will be audio recorded in order to provide supervision and fidelity checks for the interventionist. Both Group A and Group B (Control) will complete surveys assessing daily alcohol intake each morning and report blood alcohol content (via breathalyzer readings uploaded to REDCap) each evening until they have completed 42 total days of monitoring. In the unlikely event that participants are not able to upload their breathalyzer reading to REDCap, they will text a screenshot of their reading to the study coordinator on a study cell phone who will upload the reading to REDCap on the participant's behalf. Readings will be deleted from the study cell phone immediately after they are uploaded into REDCap. After all intervention/monitoring tasks are completed at 6 weeks, both groups will complete a follow-up questionnaire, which may be done in-person, online via REDCap, via phone, or via mail per participant preference. The follow-up questionnaire matches the initial baseline questionnaire, with additional questions about satisfaction with the intervention being shown to Group A (Intervention). All RCT participants will also complete a 20-30 minute semi-structured exit interview after completing the follow-up questionnaire. This interview will ask about perceptions of monitoring technology, perceived effects of monitoring, need for additional support, and suggestions for improvement. In addition to these, Group A (Intervention) participants will be asked questions regarding overall satisfaction with the TRAC program, reactions to session content, length, and components. The study coordinator will conduct the interviews. Interviews will be audio recorded and transcribed using a transcription service. Finally, 4 weeks after participants complete the follow-up survey, RCT participants will complete the delayed post-test survey at 10 weeks. This final data collection instrument matches the follow-up survey, but will not contain questions relating to satisfaction with the TRAC program. Participants may complete the delayed post-test in-person, online via REDCap, via phone, or via mail per participant preference.

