### 1.2 SAMPLE SIZE DETERMINATION

The sample size of 40 is based on the goal of estimating the probabilities and means for 3 feasibility outcome measures (enrollment  $\geq$  60% [primary], retention  $\geq$  60%, adherence [defined as  $\geq$ 70% completing at least 60% of sessions]). Assuming a negative binomial distribution and true probability of enrollment of 60%, the probability that we would have to approach 55 or more people to recruit 40 is  $<0.05$ . If we approach  $\geq$ 55 AYAs to enroll 40, it is unlikely the true probability of enrollment is 60% or greater, concluding a future efficacy study may not be feasible. Out of 40 AYAs, if the true probability of retention is 60% we expect at least 19 AYAs will be retained (i.e., probability of  $n \leq 19$  retained given true retention probability of 60% is  $<0.05$ ), so if more than 21 AYAs are not retained, an efficacy study may not be feasible. We have 80% power (using a 2-tailed alpha of 0.05) to detect an adherence proportion of 0.72 if we assume a null hypothesis adherence proportion of 0.50.

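### The 80% power for session adherence fits about 40 participants, but only the 25 in the TRAC arm have sessions; exact power there is 60%

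*Combined protocol and SAP*

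**What the plan says.** SAP section 1.2 begins: "The sample size of 40 is based on the goal of estimating the probabilities and means" for three feasibility measures: enrollment, retention and adherence. It describes adherence as at least 70% of participants "completing at least 60% of sessions". Its last sentence claims 80% power, with a two-tailed alpha of 0.05, "to detect an adherence proportion of 0.72 if we assume a null hypothesis adherence proportion of 0.50". It does not say which n that sentence uses. Section 1.3 identifies the 40 as the Aim 2 sample, and section 1.4.2.2 compares TRAC with control within Aim 2, so the 40 spans both arms.

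On who has sessions, the protocol (Study Procedures: Randomized Controlled Trial) says: "Intervention (Group A) participants will complete 4 intervention sessions on a weekly basis". For the other arm it says: "Control (Group B) participants will receive educational materials regarding alcohol use and will complete mobile monitoring of alcohol use in the same manner"; the comparison there is with the TRAC arm. On arm sizes, the Study Population section gives "Intervention group (TRAC) n=25, and Control group (education and monitoring) n= 25". The Objectives, the RCT procedures and the RCT enrollment text also give 25 per arm.

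The Objectives list a second adherence component: "intervention adherence (=70% complete =60% of intervention sessions; alcohol monitoring =70" percent. Monitoring is done by both arms: "Both Group A and Group B (Control) will complete surveys assessing daily alcohol intake each morning".

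Section 1.4.2.1 sets a hypothesized value of 70% for session adherence, and plans 95% confidence intervals and binomial tests against the hypothesized values. It does not mention 0.50.

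**The concern.** A control participant has no sessions to complete and cannot belong in a session-adherence denominator. If the 80% was computed on the two-arm total, the sample-size section claims power that the design does not have. A reader planning the definitive trial would take it that a true adherence near 72% will probably be distinguished from 50%, when the chance is much nearer to even.

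The second issue is the reference value. Power is stated against 0.50, but the test described in section 1.4.2.1 is against 70%. The power statement therefore does not describe the planned test, and the two nulls can give different readings of the same result.

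**Working it through.** **Inputs.** p0 = 0.50, p1 = 0.72, two-sided alpha 0.05, N = 40 (SAP 1.2); TRAC arm n = 25 (protocol); reference value 0.70 (SAP 1.4.2.1). All randomized TRAC participants are kept in the denominator.

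**Method.** One-sample exact binomial test with at most 0.025 in each tail. The upper limit is the smallest r with P(X ≥ r | n, p0) ≤ 0.025, and the lower limit is found likewise. Power is the probability of the rejection region under p1. As a cross-check, the normal approximation is

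power = Φ{ [(p1 − p0) − 1.96·√(p0(1 − p0)/n)] / √(p1(1 − p1)/n) }.

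**Step 1: the plan's own figure, n = 40.** The exact test rejects at 27 or more, or 13 or fewer (actual alpha 0.038). Power at 0.72 is 79.4%. Normal: [0.22 − 1.96 × 0.0791] / 0.0710 = 0.916, and Φ = 82.0%. The stated 80% is reproduced. Nearby sizes also come close (n = 37: exact 78.6%, normal 78.8%), so n = 40 is an inference from the paragraph and not something it states.

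**Step 2: the participants who have sessions, n = 25.** The exact test rejects at 18 or more, or 7 or fewer (actual alpha 0.043). Power at 0.72 is 60.0%. Normal: [0.22 − 1.96 × 0.1000] / 0.0898 = 0.267, and Φ = 60.5%.

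**Step 3: other candidate sizes, 0.72 against 0.50.**

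| n | Basis | Exact power | Normal |
|---|---|---|---|
| 20 | Assumption: SAP's 40 split 1:1 | 49.5% | 50.4% |
| 25 | Protocol's TRAC arm | 60.0% | 60.5% |
| 40 | SAP total | 79.4% | 82.0% |
| 50 | Protocol total | 86.4% | 90.0% |

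Neither TRAC-arm size gives 80%. Exact power reaches 80% at n = 42 and stays above it at every n checked up to 61; the normal approximation reaches it at n = 39.

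**Step 4: what 25 can show.**
- Smallest true adherence with 80% exact power against 0.50: about 0.77 (80.1%; at 0.76 it is 76.5%). With 20 it would be 0.80 (80.4%).
- At the SAP's own 70%, exact power against 0.50 is 51% with n = 25 and 70% with n = 40.
- If 18 of 25 adhere (72%), the Clopper-Pearson 95% CI is 0.506 to 0.879.

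**Step 5: the reference value, n = 25.** Against 0.70 the exact test rejects at 12 or fewer, or 23 or more; a true 0.72 would be rejected about 2.5% of the time. Combining this with the limits in Step 2:
- 18 to 22 adherent: excludes 0.50, not 0.70.
- 13 to 17 adherent (52% to 68%): excludes neither.
- 8 to 12 adherent: excludes 0.70, not 0.50.

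**Step 6: the session threshold.** Section 1.2 and the Objectives use 60% of sessions, while section 1.4.2.1 uses 75%. With four sessions, 0.60 × 4 = 2.4 and 0.75 × 4 = 3, so both mean at least three. The difference does not affect any figure above.

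**The case against.** This is a pilot. Its primary endpoint is enrollment, and section 1.2 describes its aim as estimation. Section 1.2 attaches feasibility conclusions to enrollment and retention but not to adherence, so the bands in Step 5 show different test results without a trial decision that would go wrong. The planned confidence intervals will show the true precision. No estimate is biased, and the protocol records the study as closed to enrollment, so recruitment cannot change. All of this stands and limits the weight of the point.

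The comparison of 80% with 60% also crosses two bases: the SAP's 40 and the protocol's 25 per arm. That is so, because the SAP gives no arm sizes and its total differs from the protocol's 50. Staying within the SAP does not help the claim, since a 1:1 split of 40 gives 49.5%. The 60% is the more favourable figure.

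Monitoring adherence applies to both arms, and a full-sample denominator is valid for it. But section 1.2 defines the adherence it powers by sessions and gives no power for monitoring.

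Finally, 0.50 may be a floor to exclude and 70% a target to hope for, which would be a coherent design. The SAP does not say so, and section 1.4.2.1 directs the test at the hypothesized value. This part is an unexplained choice that needs clarifying. It is secondary to the denominator error.

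**Conclusion.** The point holds. The power claimed for session adherence is too high for the participants to whom the measure applies: 60.0% with 25 TRAC participants against the stated 80%. The chance of missing a true 72% is therefore about 40%, twice the 20% implied. This rests on the protocol's 25 per arm, an exact two-sided test with 0.025 per tail, and all randomized TRAC participants in the denominator. That 40 lies behind the stated figure is inferred; that 25 does not support it does not depend on the inference.

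The mismatch between 0.50 and 70% is real but lesser. It should be fixed because this is a numerical claim in the sample-size justification, although its effect on the trial's conclusions is moderate.

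**What to change.** Replace the last sentence of section 1.2 with one for the TRAC arm, for example: *With 25 TRAC participants, exact power is 80% to detect session adherence of 0.77 against 0.50 (60% at 0.72), two-sided alpha 0.05.* Alternatively, state precision, which suits the estimation aim: *If 18 of 25 TRAC participants adhere (72%), the exact 95% CI is 51% to 88%.*

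Use one reference value for adherence in sections 1.2 and 1.4.2.1 and say why it was chosen. If 0.50 is meant as a floor and 70% as a target, state both roles and name the value that the test uses.

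In section 1.4.2.1, report session adherence with TRAC participants as the denominator and monitoring adherence with both arms, as separate results.

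As a separate wording matter with no effect on the power figures, reconcile the session threshold (60% or 75%) and the completion window (8 weeks in section 1.4.2.1, up to 6 weeks in the RCT procedures).

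The cost is SAP text only, with no change to design or data collection. The downside is a less favourable printed figure.

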#### 1.4.2 AIM 2 ANALYSES

##### 1.4.2.1 FEASIBILITY

Enrollment: the number of AYAs enrolled divided by the number of eligible AYAs approached (hypothesized value = 60%).

Retention the percentage of AYAs who complete baseline and follow-up questionnaires (T0, T1; hypothesized value = 60%).

Adherence: the percentage of AYAs who complete at least 75% of sessions in 8 weeks (hypothesized value = 70%); alcohol monitoring hypothesized value = 70%).

We will calculate 95% CIs for feasibility measures to determine the range of estimates that are consistent with our data. We will use one-sample negative binomial probabilities and tests of binomial proportions to compare to hypothesized values. We will summarize reasons for ineligibility and refusal and compare AYAs who drop out or do not adhere by demographic and clinical characteristics, and baseline scores of the measures (e.g., PROMIS-29, alcohol use). We will investigate differences in AYA enrollment, retention, or adherence by sociodemographic and clinical characteristics (e.g., cancer type) to identify populations for a future study.

---

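### The SAP's 80% power for adherence is computed against a null of 0.50, but the named adherence test uses 70%, and no stated rule uses 0.50

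*Combined protocol and SAP*

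**What the plan says.** Section 1.2 of the SAP opens with "The sample size of 40 is based on the goal of estimating the probabilities and means for 3 feasibility outcome measures". Its last sentence is the only power figure in the SAP. Power there is put at 80%, for a two-sided test at the 5% level, and the effect is worded as follows: "to detect an adherence proportion of 0.72 if we assume a null hypothesis adherence proportion of 0.50".

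Section 1.4.2.1 gives the adherence measure as "the percentage of AYAs who complete at least 75% of sessions in 8 weeks (hypothesized value = 70" percent, and adds "alcohol monitoring hypothesized value = 70" percent. For the analysis it says: "We will use one-sample negative binomial probabilities and tests of binomial proportions to compare to hypothesized values". It also plans 95% confidence intervals for the feasibility measures, with no limit that the interval must clear.

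The protocol's Objectives also set 70% as the adherence target. The value 0.50 appears in the power sentence and in no objective, hypothesis, named test or decision rule.

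For enrollment and retention, section 1.2 states results that would suggest an efficacy study may not be feasible. It states none for adherence.

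**The concern.** A power figure should describe the test that will be reported. Here the two sections place the burden of proof in opposite directions. Against a null of 0.50, adherence has to be demonstrated. Against a null of 0.70, a shortfall has to be demonstrated, and a non-significant result is easily read as the target having been met.

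The pilot is meant to inform whether a definitive trial is feasible. A reader who takes the 80% as applying to the comparison with 70% would overrate what that comparison can settle. A result just above one half would be reported as not significantly different from 70%, with no warning that the test had only moderate power to say otherwise.

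**Working it through.** **Inputs.** From section 1.2: n=40, two-sided alpha 0.05, null 0.50, alternative 0.72, stated power 80%. From section 1.4.2.1: reference value 0.70. From the protocol's RCT procedures: only the intervention group receives sessions, 25 of 50. Assumptions: exact binomial tests with at most 0.025 in each tail; alpha 0.05 carried over to section 1.4.2.1, which gives none; and 20 in TRAC if the SAP's 40 is split 1:1.

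**Step 1: reproduce the 80%.** With X ~ Bin(40, 0.50), P(X≥27) = 0.0192 and P(X≥26) = 0.0403, so the upper critical value is 27. Power is P(X≥27 | 0.72) = 0.794. The normal approximation gives z = [(0.72−0.50)√40 − 1.96×0.50] / √(0.72×0.28) = (1.391−0.980)/0.449 = 0.916, so power is 0.820. The stated 80% lies between the two. The arithmetic is right for those inputs.

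**Step 2: the named test, null 0.70, n=40.** P(X≤21 | 0.70) = 0.0148 and P(X≤22) = 0.0320. P(X≥34 | 0.70) = 0.0238 and P(X≥33) = 0.0553. The test therefore rejects at 21 or fewer or at 34 or more.

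- 22/40 (55%) is not rejected (p = 0.056), yet its exact 95% interval is 0.385 to 0.707.
- Showing adherence above 70% requires 34/40 = 85%. The probability of that is 28.6% at a true 0.80 and reaches 80% only at about 0.88.

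**Step 3: the named test as a check for failure.** The probability of rejecting on the low side is:

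| n | Rejects low at | True 0.50 | True 0.60 |
|---|---|---|---|
| 40 | ≤21 | 68% | 21% |
| 25 | ≤12 | 50% | 15% |
| 20 | ≤9 | 41% | 13% |

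**Step 4: a rule based on the planned interval.** The exact 95% lower limit exceeds 0.50 from 18/25 (0.506; 17/25 gives 0.465) and from 15/20 (0.509; 14/20 gives 0.457). The pass probability is P(X≥r | p):

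| TRAC n | r | 0.50 | 0.60 | 0.70 | 0.72 | 0.80 |
|---|---|---|---|---|---|---|
| 25 | 18 | 2% | 15% | 51% | 60% | 89% |
| 20 | 15 | 2% | 13% | 42% | 49.5% | 80% |

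The 80% at 0.72 thus becomes 60% or 49.5% once only the participants who receive sessions are counted.

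**The case against.** Four points on the other side have weight.

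- **The comparison with 0.50 is available.** A reader might infer that the plan never makes it. That goes too far. An exact 95% interval excluding 0.50 is equivalent to the exact test in step 1: 27/40 gives 0.509 to 0.814. What is missing is a rule attached to the interval.
- **Setting about 5% power against the stated 80%.** At n=40 the named test rejects with probability 0.043 + 0.007 = 0.050 when the truth is 0.72. That is power for a two-point difference from 0.70, which nobody planned to detect, so it is not a fair measure of the test.
- **70% may be a futility benchmark.** Section 1.2 uses 60% that way for enrollment and retention. Read so, the test has some value: step 3 gives 68% power at a true 0.50 with n=40. The 80% still belongs to a different test, and non-rejection still does not establish 70%.
- **The consequences are limited.** Adherence is a secondary feasibility outcome in a pilot sized for estimation, and the primary enrollment endpoint is untouched.

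The 27/40 case is also not a conflict between the tests: 67.5% rejects 0.50 and does not reject 0.70, and both statements can be true together.

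**Conclusion.** The point stands as a mismatch between the power statement and the named analysis. The 80% is correct for 0.72 against 0.50 at n=40, but it should not be read as power for the comparison with 70%. For that comparison at n=40, any result from 22 to 33 is inconclusive.

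A reader might go further and conclude that the planned test cannot support its target at all. The documents do not support that: the test could show adherence above 70% if the true rate were about 0.88 or more, and it can detect poor adherence with moderate power. Nor does the SAP hold two contradictory pass rules, since it states no pass rule for adherence.

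The sizes rest on exact two-sided tests at 0.05 and on n. The mismatch itself holds at any n.

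**What to change.** 1. **Section 1.4.2.1.** Keep 0.50 as the null, and state that adherence is judged by whether the planned 95% interval, computed exactly, has a lower limit above 0.50. Report the observed proportion against the 70% target, and state that non-rejection of 0.70 is not evidence of meeting it.
2. **Section 1.2.** Replace the 80% sentence with the pass probabilities from step 4 for participants who receive sessions: 18 or more of 25, or 15 or more of 20.
3. **Before fixing the cutoff, reconcile:**
   - The Aim 2 total, which is 40 in the SAP and 50 in the protocol.
   - The session threshold, which is 60% in the Objectives and section 1.2 but 75% in section 1.4.2.1. With four sessions the two coincide (0.60×4 = 2.4, so three sessions; 0.75×4 = 3). With any other number they may not.
   - The time window, which is 8 weeks in section 1.4.2.1 but 4 weeks, extendable to 6, in the RCT procedures.
4. **Alcohol monitoring.** Compute it separately. Both arms monitor, so its n is 40 or 50, and the TRAC cutoffs do not apply.
5. **Timing.** The protocol's consent section says enrollment is closed. If the rule is adopted after data were seen, label it post hoc.

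The cost is SAP wording. The stated power becomes less favourable, and the rule passes only 51% (n=25) or 42% (n=20) of the time when true adherence is exactly 70%. That should be said openly.
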